8 OBJECTIVES AND ENDPOINTS

	Objective	Endpoint	Analysis
Primary	Evaluate the safety profile of a cancer vaccine comprised of P30-linked CMV pp65, EphA2 and survivin peptides	Percent of patients who experience DLT within each stratum at each dose level	See Section 15.5
Secondary	Assess whether pp65-specific polyfunctional T cells increase after priming vaccination with the P30-linked pp65 peptide.	Among CMV seropositive patients, mean fold increase in pp65-specific T cells between day 1 and day 22 in patients, and day 1 and 84. Among CMV seronegative patients, percent of patients who develop pp65-specific polyfunctional T cells between day 1 and 22, and day 1 and 84.	See Section 15.6.1
Secondary	Assess whether EphA2- or survivin-specific polyfunctional T cells increase after priming vaccination with P30-linked EphA2 or survivin peptides.	Among all patients, mean fold increase in EphA2- or survivin-specific T cells between day 1 and day 22, and day 1 and 84	See Section 15.6.2
Secondary	Assess whether pp65-specific polyfunctional T cells increase after booster vaccination with the P30-linked pp65 peptide.	Among CMV seropositive patients, mean fold increase in pp65-specific T cells between day 84 and day 140. Among CMV seronegative patients, percent of patients who develop pp65-specific polyfunctional T cells between day 84 and day 140.	See Section 15.6.3
Secondary	Assess whether EphA2- or survivin-specific polyfunctional T cells increase after booster vaccination with P30-linked EphA2 or survivin peptides.	Among all patients, mean fold increase in EphA2- or survivin-specific T cells between day 1 and day 84 and 140.	See Section 15.6.4

	Objective	Endpoint	Analysis
Other Secondary	Describe the survival and PFS of patients who received a vaccine comprised of P30-linked pp65, EphA2 and survivin peptides.	Median survival Median PFS	See Section 15.6.5
Exploratory	Assess the diversity of the P30-EPS-specific memory T cell repertoire via TCR sequencing.	Median change in normalized entropy between baseline (pre-vaccine #1) and after vaccine #5. Entropy is a measure of clonal expansion, or the extent of TCR repertoire expansion.	See Section 15.7.1

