15.7 Exploratory Objectives

This study has four main exploratory objectives: (1) Assess the diversity of the P30-EPS-specific memory T cell repertoire via TCR sequencing, (2) Define the relationships between reported biomarkers of response to immunotherapy in GBM and survival, (3) Assess resected tumor for the expression of vaccine targets (i.e. EphA2, pp65, and survivin), and (4) Assess changes in the tumor immune microenvironment, mutational heterogeneity/clonality, neoantigen depletion, and their association with survival.

Additional objectives which are not explicitly stated here may also be explored. These additional analyses will be motivated by the results of analyses addressing the objectives stated a priori, as well as changes or new additional to the clinical literature.

15.7.1 Exploratory Objective: Diversity of the P30-EPS-specific memory T cell repertoire via TCR Sequencing

Objective: Assess the diversity of the P30-EPS-specific memory T cell repertoire via TCR sequencing

Analysis Set: Patients who have samples available for TCR analyses at baseline and after 5 P30-EPS vaccines

Outcome: Change in normalized entropy of P30-EPS-specific T cell clonotypes between baseline and post-vaccine 5

Hypothesis: P30-EPS vaccination will broaden the number of different T cell clones recognizing a single antigen

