Analysis Plan: Patients' samples will be divided into two aliquots: one will be directly sequenced to record the overall repertoire; the other will be stimulated and expanded by the designated P30-EPS for 7 days and then sequenced. The raw sequencing reads from baseline (before vaccine #1) and an assessment after vaccine #5 will be stored in fastq files and pre-processed using the IMSEQ [67] software using reference barcode sequences from International Immunogenetics Information System [68]. TCR sequences are characterized by aligning the input to the reference V, D and J regions as well as the random regions. We will focus on the TCR beta-chain. To control alignment qualities, we will exclude reads with average quality score below 10. After the pre-processing step, the IMSEQ software will produce the clone-types of T cells. We will then derive the clonotypes and their relative frequencies. Clones which have fewer than 20 reads or 0.5% of total reads will be excluded. Alternatively, we will leverage a new method we developed to perform error-tolerance mapping. This method will not only produce the mapping results, but also assign a posterior probability to each read that measures how likely it belongs to a clone type.

With the P30-EPS-stimulated samples, we will perform Motif analysis to enrich P30-EPS-specific TCR clonotypes. All TCR clonotypes from the sequencing will be

included to generate all possible amino acid motifs with varying lengths using the R *tcR* package. Two separate pools of CDR3 sequences were created initially for each of these motifs from directly sequenced aliquot and P30-EPS-stimulated aliquot. To account for different sequence depths across samples, we will normalize the number of CDR3s containing each motif by the total number of CDR3s containing all motifs in each sample. The motif frequency ratios between directly sequenced aliquot and P30-EPS-stimulated aliquot will be compared. A higher ratio represents more abundant motifs in P30-EPS-stimulated aliquot compared with directly sequenced one, enabling the identification of a set of candidate motifs as P30-EPS-specific. The importance of each motif will be evaluated using both Mean Decrease Accuracy and Mean Decrease Gini in the random forest. A standard receiver operating characteristic (ROC) approach will be applied to evaluate the predictive power of each motif. These analyses will be performed using R *randomForest* [69] and *ROC* packages.

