After the P30-EPS-specific CDR3 motifs are identified, we will map these motifs back to each individual TCR clones within the directly sequenced PBMC samples. These TCR clones will be considered to be P30-EPS-specific. For a given clone type, we will sum up all the read posterior probabilities if they exceed 0.2, and record the sum as the weighted frequency of the clone type. To test for overall clonal expansion, we will calculate the normalized entropy of the clonotypes at each time point. A decrease in entropy implies a decrease in diversity in clonotypes, and subsequently the expansion (increase in frequency) of one or more specific clonotypes. For each patient, the change in entropy over time will be computed. A Wilcoxon signed rank test will assess whether diversity has increased with vaccination.

15.7.2 Exploratory Objective: Define the relationship between reported biomarkers of response to immunotherapy in GBM and survival

Objective: Define the relationship between reported biomarkers of response to immunotherapy in GBM and survival

Analysis Set: Any available tumor tissue from patients on-study prior to and/or after immunotherapy with P30-EPS vaccine

Outcome: Association between the following: TMB, tumor-intrinsic Erk1/2 signaling, TMEM119+ (microglia) cell density, peripheral Ki67+ CD8 T cells, and gene expression signatures of MHC-class II, IFN- γ , and cell cycle/proliferation

Hypothesis: In patients with higher TMB, increased immune activation (Ki67+ CD8 T cells, MHC-class II, IFN- γ), and lower Erk1/2 signaling and microglial density, P30-EPS vaccination is more likely to enhance the antitumor immune response.

Analysis Plan: The following biomarkers that have been reported to be predictive for response to immunotherapy in GBM, will be assessed on surgically resected tumor

tissue using the noted approaches, including quantitative immunohistochemistry (qIHC), bulk RNAseq, and whole exome sequencing (WES):

- MEK-ERK activating mutations - WES; Zhao et al Nat Med 2019 [70]
- High frequency of p-ERK+ tumor cells - qIHC; Arrieta et al Nat Cancer 2021 [71]
- High MHC-class II gene expression - RNA-seq; Arrieta et al Nat Cancer 2021 [71]
- IFN γ signature; Cell cycle gene signature repression - RNAseq; Cloughesy et al Nat Med 2019 [72]
- Exhaustion signatures, inhibitory receptors - RNA-seq, qIHC; Lee et al. Nat Comm 2021 [73]
- Putative neoantigen depletion - WES, RNA-seq; Gromeier et al Nat Comm. 2021; preliminary data [74]

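### The T cell receptor diversity endpoint does not directly measure its own hypothesis and can move in the wrong direction

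*Combined protocol and SAP*

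**What the plan says.** All of this is in the combined protocol and SAP, mainly Section 15.7.1.

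- **Hypothesis:** "P30-EPS vaccination will broaden the number of different T cell clones recognizing a single antigen".
- **Outcome:** "Change in normalized entropy of P30-EPS-specific T cell clonotypes between baseline and post-vaccine 5". The endpoint table in Section 8 summarises it as a median change and adds: "Entropy is a measure of clonal expansion, or the extent of TCR repertoire expansion". Neither place gives the normalizer.
- **Purpose of the index:** "To test for overall clonal expansion, we will calculate the normalized entropy of the clonotypes at each time point".
- **Reading of a fall:** "A decrease in entropy implies a decrease in diversity in clonotypes, and subsequently the expansion (increase in frequency) of one or more specific clonotypes".
- **Test:** "A Wilcoxon signed rank test will assess whether diversity has increased with vaccination". No alpha level or sidedness is stated for it.
- **Filter:** after clonotypes are called with the IMSEQ software, "Clones which have fewer than 20 reads or 0.5% of total reads will be excluded". The plan then offers an alternative, in-house mapping method that gives each read a posterior probability, and states no frequency filter for it. The clone weights recorded just before the entropy step are sums of such posterior probabilities.
- **Sample:** specific clones are identified by mapping motifs back to the PBMC aliquot that was sequenced without stimulation.

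Section 15.7.1 plans no clone count or other measure of richness.

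**The concern.** The hypothesis concerns richness, that is, how many different clones recognise an antigen. Normalized entropy, as usually defined, concerns evenness, that is, how equally the reads are spread over the clones present. The two can move in opposite directions.

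The plan also attaches two meanings to one index. A fall is its sign of clonal expansion, which is a plausible vaccine effect, and it is also evidence against the stated hypothesis. With no expected sign fixed in advance, either result could be presented afterwards as a vaccine effect.

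Finally, a floor set as a share of total reads removes low-frequency clones, and newly recruited clones are likely to be among these. At stake is whether the first exploratory objective gets an interpretable answer.

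**Working it through.** The plan gives no power, sample size or alpha for this endpoint, so there is no figure of its own to reproduce. The only numerical inputs it supplies are the 20-read and 0.5% limits. The repertoires below are illustrative.

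**Definitions.** For clone shares p, Shannon entropy is H = −Σ p ln p. With K the observed clone number, three scales are compared: H/ln(K), assumed here as the usual meaning of normalized entropy; H/ln(200), as one example of a fixed normalizer; and exp(H), the effective number of clones.

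**Step 1: equal clones.** For K equal clones H = ln(K), so H/ln(K) = 1.00 whatever K is. On the fixed scale, 10, 20, 50, 100 and 200 equal clones score 0.435, 0.565, 0.738, 0.869 and 1.00.

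**Step 2: more clones, three cases, each starting from 10 equal clones** (H = ln 10 = 2.303).

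| After vaccination | H | H/ln(K) | H/ln(200) | exp(H) |
|---|---|---|---|---|
| 40 equal clones | ln 40 = 3.689 | 1.00 to 1.00 | 0.435 to 0.696 | 10 to 40 |
| 40 clones, one at 50% | ln 2 + 0.5 ln 39 = 2.525 | 1.00 to 0.68 | 0.435 to 0.477 | 10.0 to 12.5 |
| 30 clones, 20 new ones at one-tenth size | 2.869 | 1.00 to 0.84 | 0.435 to 0.541 | 10.0 to 17.6 |

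The clone number triples or quadruples in every row. H/ln(K) stays flat or falls; the other two scales rise.

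**Step 3: other movements of H/ln(K).**

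- Narrowing: 5 large and 5 rare clones (one-tenth size) losing the 5 rare ones goes from 0.83 to 1.00, a rise.
- Broadening from an uneven start: 10 clones, one of them 10 times the rest, gaining 10 clones goes from 0.75 to 0.86 if the new clones are small and to 0.88 if they are large, a rise.
- Dominant expansion: one of 10 equal clones growing 10-fold goes from 1.00 to 0.75; one of 50 growing 20-fold goes from 1.00 to 0.86.
- Uniform expansion: all clones growing 10-fold leaves 1.00.
- Minor clones expanding: in the uneven 10-clone repertoire, the nine small clones growing 5-fold goes from 0.75 to 0.99.

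**Step 4: filter, where it applies.** Each retained clone must hold at least 0.5% of reads, so at most 1/0.005 = 200 clones survive per sample. The 0.5% limit is stricter than the 20-read limit above 20/0.005 = 4,000 total reads. Specific clones share these places with all other T cell clones. If they hold a share s of total reads, at most s/0.005 survive: 2, 10, 20 or 50 for assumed shares of 1%, 5%, 10% or 25%.

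**The case against.** The strongest reply is that the normalizer used above is an assumption. The plan never says that entropy is divided by the log of the observed clone number, and under a fixed normalizer every case in Step 2 moves the right way. This stands. It changes the defect from a wrong index to an undefined one whose sign depends on the definition.

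A reader might go further and infer that the endpoint cannot test its hypothesis, that pure broadening always gives no change, or that clonal expansion is always scored as lost diversity. The documents do not support this. Even under H/ln(K), Step 3 shows that broadening can raise the index, that uniform expansion is neutral and that growth of minor clones raises it. Only expansion dominated by one or a few clones is scored as loss.

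A reader might also take the 200-clone cap as settled. It follows the IMSEQ step only, whereas the weights recorded just before the entropy step are described only for the alternative route, for which no filter is given.

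It is also fair to say that entropy is a legitimate diversity index and fits the objective, which is to assess diversity; the clash is with the hypothesis sentence and the stated direction. Section 15.7 allows further exploratory analyses, so a count could be added later. A count chosen after the entropy result is known would, however, carry less weight than one named now.

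The inconsistency of direction needs no assumption about the normalizer, and nothing in the reply removes it.

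**Conclusion.** The point holds in limited form. Section 15.7.1 states a hypothesis about clone number, plans no analysis of clone number, and relies on an index whose normalizer is undefined. On the usual definition that index can stay at 1.00 when clones quadruple, or fall to 0.68, while a fixed normalizer gives a rise in both cases. The plan ties a fall to expansion and then tests for an increase in diversity, and Section 8 calls the index a measure of expansion without giving a sign. Which mapping route and filter feed the entropy step is not stated; on the IMSEQ route the filter works against detecting new low-frequency clones.

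The numerical results rest on illustrative repertoires, on H/ln(K) as the usual definition, and, for the specific-clone limits, on assumed read shares. They show that the sign can be wrong, not that it will be. The endpoint is exploratory, so this should be corrected before the sequence data are analysed, but it does not bear on dose escalation, the primary safety objective or the sample size.

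**What to change.** 1. Test the broadening hypothesis on the within-patient change in the number of distinct P30-EPS-specific clonotypes, or the effective number exp(H), at a common down-sampled read depth, using the planned Wilcoxon signed rank test. The count is the more direct choice, because exp(H) still responds to evenness: one of 10 equal clones growing 10-fold takes it from 10.0 to 5.7 with no clone lost.
2. Keep normalized entropy as a separate, two-sided measure of clonal expansion. Define its normalizer, and make the meaning of a rise and a fall consistent between Section 8 and the outcome, hypothesis and analysis plan of Section 15.7.1.
3. State which mapping route supplies the clone frequencies and whether the 20-read and 0.5% limits apply to it.
4. Report the clone count with and without the 0.5% filter as a sensitivity analysis. Removing the filter outright is not advised: at an assumed 1,000,000 reads the floor would drop from 5,000 reads to 20, and sequencing error could then look like broadening.

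The cost is SAP wording and an added analysis of sequence data already planned. The drawback is that clone counts are more sensitive to sequencing error and to the number of input cells, and down-sampling reads does not equalise cells.

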15.1 Study Design Overview

Adults with newly diagnosed, primary GBM who are IDH wild type, have unmethylated MGMT promoter, and have undergone resection will be eligible for this study. Patients who meet eligibility criteria will be offered enrollment at the clinic visit after XRT/TMZ if they can start treatment within 8 weeks of XRT/TMZ completion (and as long as this is felt to be in the best interest of the patient by the treating physician). A maximum of 36 patients will be accrued to this study. After the initial dose escalation portion is complete, patients will be tested for CMV status however enrollment will be first come, first serve, and the slots will not be allocated based on CMV results.

All patients will receive P30-EPS vaccine (EphA2, pp65, and survivin peptides each linked to P30) suspended in 10% DMSO in water, pooled, and mixed with 20 µg/kg of Hiltonol®. All P30-EPS vaccines are given initially in a Priming Phase [on days 1, 4 (\pm 1 day), 8 (\pm 1 day), 15 (\pm 2 days), and 22 (\pm 2 days)], and then in a Booster Phase (on day 84 and day 140, both \pm 7 days).

The primary objective of this trial is to evaluate the safety of P30-EPS vaccines in patients with newly diagnosed GBM, while exploring the impact of the treatment regimen on the immunologic response of the patient.

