MEK-ERK activating mutations will be queried using existing WES data. qIHC will be performed for p-ERK1/2 and TMEM119 as described by Arrieta et al *Nature Cancer* 2021 [71].

To define T cell exhaustion/inhibitory receptors, we will also similarly quantify and define spatial PD-L1, CTLA4, PD1, TIGIT, and TIM3 expression in all tumor samples, using qIHC. Bulk RNA-seq data will be used to determine MHC-class II, IFN γ and cell cycle gene expression signatures, as well as differential expression of inhibitory receptors (TIGIT, TIM3, CTLA4, and PD1).

Neoantigen depletion will be predicted using the pVAC-seq pipeline. Briefly, for the pVAC-seq pipeline, neoantigens will be defined at 8-11-mer peptides from exonic nonsynonymous single nucleotide variants that bind to a patient's respective HLA class I molecule with a binding affinity score <500nM stronger than the wildtype peptide using NetMHCpan51. Neoantigen density will be expressed as ratio of observed to expected neoantigens. Expected neoantigen levels will be determined using a previously empirically derived rate of mutation that assumes no selection against neoantigen-causing mutations normalized to the silent mutation load for each patient's tumor [75]. MHC class I epitope predictors are imperfect in predicting actual MHC class I binding epitopes [76]. Thus, nonsynonymous mutation/TMB ratios will also be used to predict neoantigen depletion: lower non-synonymous mutations out of total mutations is surrogate measure of neoantigen density [77].

Each feature will be tested for its association with post- P30-EPS vaccine survival to determine if other biomarkers are superior in identifying P30-EPS vaccine responsive GBM patients. We will also test the relationships between each biomarker to determine if they identify the same patients, and to further define the nature of patients living longer after P30-EPS vaccination.

The associations between the various biomarkers will be explored with scattergrams, and correlation (Pearson or Spearman) with adjustment for multiple comparisons. For each biomarker, Receiver-operating curves will be performed to

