15.9 Sample Size Calculation

The primary correlative analysis in this study will assess immune outcome at Day 140. To address these analyses, we intend to treat a sufficient number of patients with vaccine at its MTD so that approximately 18 patients will provide immune outcome data at Day 140. Based upon Stupp[6], we crudely estimate that approximately 75% of treated patients will provide Day 140 data. Hence, we anticipate that we will treat 24 patients at the vaccine's MTD. We anticipate that two-thirds of these patients treated will be CMV seronegative.

Prior to the determination of the vaccine MTD, additional patients may be treated at other dose levels. We anticipate that no more than 12 more patients (6 CMV seropositive and 6 CMV seronegative) will be treated at dose levels other than the MTD. Hence, no more than 36 patients will be accrued to this study.

Patients who withdraw from study participation before initiation of vaccine treatment will not be counted towards this accrual goal. Power calculations for selected secondary study endpoints may be found in Section [15.6.1](#) and [15.6.2](#).

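### Section 15.7.2 reads survival association in a single vaccinated arm as vaccine responsiveness, with no safeguard against a purely prognostic marker, and does not test its own immune-response hypothesis

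*Combined protocol and SAP*

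**What the plan says.** Section 15.7.2 sets out to relate reported biomarkers of immunotherapy response to survival. Its analysis plan tests each feature against survival after vaccination "to determine if other biomarkers are superior in identifying P30-EPS vaccine responsive GBM patients". It then adds ROC cut-offs for short versus long survival, a joint Cox model on survival, and correlations among the biomarkers.

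The hypothesis in the same section is about something else. In patients with higher TMB, more immune activation, and "lower Erk1/2 signaling and microglial density", it expects that "P30-EPS vaccination is more likely to enhance the antitumor immune response". The list of reported predictors that follows includes "High frequency of p-ERK+ tumor cells" and MEK-ERK activating mutations.

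On design, Section 15.1 states "All patients will receive P30-EPS vaccine" and "A maximum of 36 patients will be accrued to this study", and Section 9.1.9 gives randomization as not applicable. Section 15.9 adds "we anticipate that we will treat 24 patients at the vaccine's MTD", with the aim that "approximately 18 patients will provide immune outcome data at Day 140". Section 9.3 warns that the sample is too small for firm conclusions on these features and calls the findings hypothesis generating.

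**The concern.** Section 15.7.2 defines vaccine responsiveness by nothing except survival. It specifies no control comparison and no adjustment for known prognostic factors. Its inputs are a biomarker and a survival time in patients who were all vaccinated, so the result does not depend on whether the vaccine works. A marker that predicts survival under any treatment could be reported as identifying vaccine responders.

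The written hypothesis, which concerns immune response, is left without an analysis in its own section, although antigen-specific T-cell changes are already measured under Section 15.6. Because the Erk1/2 direction is stated both ways, an association of either sign could be presented as supportive.

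**Working it through.** **1. Sample size from the plan.** Section 15.9: 18 / 0.75 = 24 patients at the MTD, and 24 + 12 at other doses = 36. Both figures reproduce, so the illustrations below use n = 24 and n = 36.

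**2. What one arm can estimate.** Write the log hazard ratio for marker x and vaccine indicator v as b1·x + b2·v + b3·x·v. Here b1 is prognosis and b3 is a vaccine effect that depends on the marker. With v = 1 for everyone, the slope on x is b1 + b3 and the two terms cannot be separated. A purely prognostic marker (b3 = 0, b1 ≠ 0) gives a non-zero slope. This step needs no assumed number.

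**3. Size, continuous marker, zero vaccine effect.** Assumptions: exponential survival with median 14 months, uniform censoring at 12-48 months (about 73% events), two-sided Cox p < 0.05, a biomarker value for every patient, and 600 simulated trials per cell. The Monte Carlo standard error is at most √(0.25/600) = 2 percentage points. Ranges are across repeated runs.

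| Prognostic HR per SD | n = 24 | n = 36 |
|---|---|---|
| 1.5 | 30-32% | 48-49% |
| 1.75 | 54-56% | 74-75% |
| 2.0 | 70-74% | 88-89% |

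With no prognostic value (HR 1.0) the test is positive in 5-6% of trials.

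**4. Cross-check, binary marker split 50/50.** Schoenfeld: power = Φ(√(d/4)·ln HR − 1.96), with d events.
- HR 2, d = 24: √6 × 0.693 − 1.96 = −0.26, giving 0.40.
- HR 2, d = 36: 3 × 0.693 − 1.96 = 0.12, giving 0.55.
- HR 1.5: 0.17 and 0.23. HR 3: 0.77 and 0.91.

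A log-rank simulation (14-month median, censoring at 36 months) gives somewhat lower values for HR 2: 0.34 at n = 24 and 0.47 at n = 36. The direction is the same and the level depends on the marker.

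**5. Contrast.** In a hypothetical 1:1 controlled design with 36 per arm, a marker-by-treatment interaction test is positive in 3.8%, 3.8% and 5.0% of trials at prognostic HR 1, 2 and 3. That test is not misled by prognosis, but this trial cannot run it.

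**6. Hypothesis against analysis.** The hypothesis outcome is enhancement of the antitumor immune response. The outcomes analysed in 15.7.2 are survival (association tests, ROC, Cox) and correlations among biomarkers. The 15.6 fold changes and responder endpoint do not appear. Section 15.7.4 examines expression changes after vaccination, but only with tissue from a second surgical procedure. It is framed on low TMB or longer survival, whereas the 15.7.2 hypothesis names higher TMB.

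**7. Erk1/2 direction.** The hypothesis favours lower Erk1/2 signaling. The predictor list names a high p-ERK+ frequency and activating MEK-ERK mutations, which point towards higher signaling.

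**The case against.** The stated objective of 15.7.2 is the relationship between biomarkers and survival, and the survival analyses answer it. The overreach lies in one purpose clause and a mismatched hypothesis. That is fair, and it is why rewording plus one table is enough.

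Section 9.3 already calls the findings underpowered and hypothesis generating. That limits the harm but concerns precision, not what is estimated. In step 3 the misleading result becomes more frequent as n rises from 24 to 36.

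The p < 0.05 rule, hazard ratios, median and censoring are assumptions. The plan speaks only of testing and states no threshold for declaring a marker. Tissue will not be available for everyone, and any multiplicity adjustment would lower the rates. The percentages therefore illustrate and do not predict.

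Several stronger readings are tempting and not supported:
- *Every prognostic marker would pass.* At HR 1.5 per SD most trials of 24 miss it, and about half do at 36.
- *The hypothesis is tested nowhere.* Section 15.7.4 gives partial coverage in paired tissue, and Section 15.7.3 relates T-cell inflammation after vaccination to antigen expression. Section 15.7.2 itself includes peripheral Ki67+ CD8 T cells among its features, without stating when they are sampled.
- *The result will select patients for a later trial.* The only future restriction mentioned is HLA-A*0201 status (Section 12.1), and no dose or stopping decision uses 15.7.2.

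**Conclusion.** The concern holds in limited form. In a single vaccinated arm, the 15.7.2 analyses estimate prognostic and vaccine-dependent effects together, and nothing in the section guards against reading the first as the second. That conclusion is structural and rests on no assumed number. Its size does: with zero vaccine effect, about 30-50% positive at HR 1.5 per SD and 70-90% at HR 2.0 for n = 24 to 36, under the inputs in step 3, and fewer with less tissue.

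The section's immune-response hypothesis is not tested within 15.7.2 and is touched in 15.7.4 only for patients with a second resection. The Erk1/2 direction conflict stands on the text alone. None of this affects the primary safety objective.

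**What to change.** In Section 15.7.2:

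1. Describe the survival, ROC and Cox results as prognostic associations in vaccinated patients, and delete the claim of superiority in identifying vaccine-responsive patients.
2. Add an exploratory rank-based analysis of pre-vaccine biomarkers against the Section 15.6 immune outcomes.
   - Use log fold change for EphA2 and survivin in all patients, and for pp65 in CMV seropositive patients only.
   - For pp65 in seronegative patients use the 15.6.1 responder endpoint, descriptively. Section 15.9 expects two-thirds of the 24 MTD patients to be seronegative (16, leaving 8 seropositive). At the 2.5% response rate cited in 15.6.1, 16 × 0.025 = 0.4 responders are expected.
   - Report by HLA-A*0201 status where known, because the epitopes are restricted to that type (Section 7.2) while all types are eligible (Section 12.1).
3. Reconcile the Erk1/2 direction between the hypothesis and the predictor list.

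The cost is SAP wording and one extra table from data already collected. The survival claim becomes more modest. The new table will be low-powered and hypothesis generating, with about 18 patients expected to have Day 140 data.
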